5.1.2.2 Description of Studies

5.1.2.2.1 Human Cytokine Assays

Human multiplex inflammatory cytokine ELISA (Meso-Scale Discovery, Gaithersburg, MD: Cat.# K15008), human IL-5 ELISA (Cat.# K111AJA), VEGF ELISA (Cat.# K111BMA), RANTES (Cat.# K111BFA) and IP-10/CXCL-10 (Cat.# K111AVA) will be performed in the AIDS Monitoring Laboratory, Leidos Biomedical Research Inc., Frederick.

5.1.2.2.2 Viral IL-6 Assay

Performed in the laboratory of [name], using a modification of the method previously described by our group([69](#)).

5.1.2.2.3 KSHV Serology, KSHV Viral Load, and KSHV Specific T-cell Responses

Performed in the laboratory of [name], Leidos Biomedical Research Inc., Frederick, using methods previously described by her group([19](#)).[\(149-151\)](#)

5.1.2.2.4 HIV Viral Load Single Copy Assay

Performed in the laboratory of [name], NCI, using real-time reverse transcriptase-initiated PCR assays previously described by his group([152](#)).

5.1.2.2.5 Monocytes and T-cell Activation, Stimulation and Subset Assays

Performed in the laboratory of [name], NIAID. Assays of monocyte activation and T cell polyclonal stimulation and activation, including HLA DR/38/Ki67/PD-1/CD57/Ro/CD27/FoxP3/CD25 will be performed by flow cytometry.

5.1.2.2.6 Systemic Angiogenesis Assays

Performed in the laboratory of [name], NCI. Assays of FGF-2, Dll4/Notch and Ephrinb2/Ephb2 will be performed by ELISA and/or Western blot on blood samples.

5.1.2.2.7 KS Tissue Angiogenesis and Signaling Assays

Performed in the laboratory of [name], NCI.

Assays of the Notch ligands Dll1, Dll3, Dll4, Jag1 and Jag2; the Notch receptors Notch1,2, 3 and 4; Notch intracellular domain (ICD); the Notch target genes Hey1 and Hey2; the transcription factors ZEB1, ZEB2, Slug and snail; EphrinB2 and EphB receptors; and markers of NFkB activation p65, p50IkBalpha and IKK1 will be performed using mRNAs for quantitative PCR, Westerns blots, and immunohistochemistry for confocal microscopy.

5.1.2.2.8 KSHV RNA and Protein Expression Analysis

Performed in the laboratory of [name], HAMB, CCR, NCI. After cell separation, cells will be lysed to extract RNA and protein. These samples will be analyzed using quantitative PCR, gene expression arrays and Western blots with a focus on KSHV miRNA target genes.

5.1.2.3 KS Tumor Biopsies

5.1.2.3.1 From screening material

If additional research tests are to be performed on the screening biopsy (see Section 2.2.5.2.2), please divide the specimen remaining after sufficient tissue for diagnostic purposes has been submitted to Laboratory of Pathology in formalin for histopathology and immunohistochemistry and distribute in the priority indicated in Section 5.1.2.3.3.

5.1.2.3.2 Additional optional biopsies:

5.1.2.3.2.1 On therapy biopsy

Where there is cutaneous disease, an optional biopsy for research purposes may be performed during the treatment phase on day one of cycle three (or day 28 of cycle two if this is more convenient). A 2-3mm cutaneous punch biopsy only will be obtained. Where an on-treatment research biopsy is obtained, the specimens will be handled as follows, in this priority:

- Place sufficient tissue for diagnostic purposes directly into formalin and submit to Laboratory of Pathology for histopathology and immunohistochemistry including KSHV-LANA and KSHV-vIL-6.
- Divide the remainder and provide to the 1. [name] laboratory (fresh, on gauze damp but not wet with saline, at 4°C) for tissue expression of Dll4/Notch, Jag1/Notch, Jag2/Notch, Notch ICD (intracellular domain), Hey1/Hey2 and EphrinB/EphB, and markers of NFkB activation (including p65, p50IkBalpha, IKK1)

5.1.2.3.2.2 Post-therapy biopsy

Additional optional 6 mm cutaneous punch biopsies may be performed in one or both of the following two circumstances if clinically indicated: after therapy has been completed, if clinically indicated and subject to patient agreement, to confirm clinical complete response; or during therapy to document progressive disease if there is clinical uncertainty about new lesions. Where such biopsies are obtained, the specimens will be handled as follows, in this priority:

- Place sufficient tissue for diagnostic purposes directly into formalin and submit to Laboratory of Pathology for histopathology and immunohistochemistry including KSHV-LANA and KSHV-vIL-6.
- Divide the remainder and distribute in the priority indicated in Section 5.1.2.3.3

5.1.2.3.3 Distribution of Biopsy Material

1. [name] laboratory (fresh, on gauze damp but not wet with saline, at 4°C) for tissue expression of Dll4/Notch, Jag1/Notch, Jag2/Notch, Notch ICD (intracellular domain), Hey1/Hey2 and EphrinB/EphB, and markers of NFkB activation (including p65, p50IkBalpha, IKK1)
2. [name] laboratory (frozen, on dry ice or trizol) for KSHV gene expression

3. [name] laboratory (fresh, on saline-soaked gauze, at 4°C) for KSHV RNA and protein expression analysis with a focus on KSHV miRNAs and miRNA target gene evaluation
4. For any residual tissue, freeze as soon as possible for storage at -40°C and send via messenger to the AIDS Monitoring Laboratory (AML), Leidos Biomedical Research Inc., at NCI-Frederick (see Section [5.2](#)).

5.1.2.4 Biospecimens for storage

Assays will be performed in batches with the exception of monocyte functional assays and pharmacokinetic testing. Samples for the batched correlative studies above will be sent via messenger to the AIDS Monitoring Laboratory (AML), Leidos Biomedical Research Inc. in the NCI-Frederick (See Section [5.2](#)) for storage until assays are performed. Collection schedule and sample requirements are given in Section [3.4](#), and Section [5.1.2.1](#).

5.2 SAMPLE STORAGE, TRACKING AND DISPOSITION

It is understood that per the NCI policy regarding the Requirements for the Research Use of Stored Human Specimens and Data, prospective NIH IRB approval and continuing IRB oversight must be obtained for research involving identified or coded samples or data where investigators can identify the source. This policy applies to research protocols where the remaining research activities are limited to data analysis and to the subsequent research use of specimens or data previously collected under a now terminated protocol. The following guidelines describe how these principles apply to this specific protocol.

- AIDS Monitoring Laboratory, Science Applications International Corporation
 - Many samples on this study will be processed and stored in the AIDS Monitoring Laboratory (AML) run by Leidos Biomedical Research Inc. in the NCI-Frederick facility located with Fort Detrick. The samples are stored under code, and the information linking these unique codes to the subjects is kept on the AML database. The laboratory informatics system conforms to NIH Information Technology Security Requirements and NIH Protection of Human Research Subjects Guidelines. All laboratory staff is trained to adhere to NIH Information Technology Security Requirements and NIH Protection of Human Research Subjects Guidelines. Computers used to access inventory systems require username and password for login. The laboratory database is housed in a secure, protected environment and backups are performed routinely. Access to specimen information, clinical data, and stored specimens is limited to approved laboratory staff and the investigator in charge of the study (or individuals authorized by the investigator).
- Specimen Withdrawal for Research Purposes
 - The protocol team will inform the AML staff when tests are to be run with the specimens, and the samples used for testing will be tracked by the AML. This information will in turn be shared with the protocol team. The research nurse on the study will be in charge of tracking this information for the protocol team.
- Specimens Sent to the [name] Laboratory
 - Some of the specimens are sent to the laboratory of [name], also in Leidos Biomedical Research Inc., in the NCI-Frederick facility located with Fort Detrick. This is a locked laboratory, and a log is kept of the specimens and when they are

- A limited number of samples are sent to [name] laboratory. This is a locked laboratory, and a log is kept of the specimens and when they are utilized. The samples sent are coded by the protocol research team and have no patient identifiers. They are logged in by [name] laboratory and are run in batch when enough specimens are collected. Records are kept when the specimens are used for analysis.

[name]
[name]
[name]
Bethesda, MD
[contact]

➤ Clinical Testing of Stored Specimens

- Clinical testing of all samples will be one in accordance to the protocol. The protocol team will inform the AML staff when tests are to be run with the specimens, and the samples used for testing will be tracked by the AML. This information will in turn be shared with the protocol team. The research nurse on the study will be in charge of tracking this information for the protocol team.

➤ Clinical Center Processing and Storage of Clinical Specimens

- Many routine samples and a sample of the biopsy specimens are sent to the Laboratory of Pathology (CCR), Department of Laboratory Medicine, and Department of Transfusion Medicine at the NIH Clinical Center. These samples will be handled according to the procedures of these departments. Results for clinical testing are generally available via the CRIS electronic medical record.

➤ Co-enrollment on 01-C-0038

- If subjects have co-enrolled on study 01-C-0038 (Collection of Blood, Bone Marrow, Tumor, or Tissue Samples from Subjects with HIV Infection, KSHV Infection, Viral-related Pre-Malignant Lesions, and/or Cancer), then the samples may also be tested under the specifications of that study. Similarly, if subjects have co-enrolled on other studies approved by the NIH Intramural IRB that call for maintaining and testing the samples, then they may be transferred to those studies.

➤ Handling of Specimens at Study Termination

- At the termination of the protocol, if subjects have co-enrolled on study 01-C-0038 (Collection of Blood, Bone Marrow, Tumor, or Tissue Samples from Patients with HIV Infection, KSHV Infection, Viral-related Pre-Malignant Lesions, and/or Cancer), then the samples will be transferred to that study unless the patient requests that this not occur. Also, if subjects have co-enrolled on other studies approved by the NIH Intramural IRB that call for maintaining the samples, then they will be maintained on those protocols. Otherwise, the unused samples will be destroyed.

➤ Loss or Destruction of Samples

- The Principal Investigator will record any loss or unanticipated destruction of the samples as a deviation. Reporting will be per the requirements of Section 7.2.

6 DATA COLLECTION AND EVALUATION

6.1 DATA COLLECTION

- Members of the HIV/AIDS Malignancy Branch clinical research team will collect data on study subjects according to the Schedule of Evaluations outlined in Section 3.4. Complete records will be maintained on each patient including supplementary information obtained from outside laboratories, radiology reports, or physician's records. These will serve as the primary source material that forms the basis for the research record. The primary source documentation will assure the following:
 - The patient satisfied each eligibility criterion.
 - Signed informed consent was obtained prior to registration and treatment.
 - Treatment was given according to protocol or any protocol violations documented and justified.
 - Toxicity and response were assessed according to protocol.
 - Drug accountability records were kept on each patient.
- Clinical data will be coded for database entry. Data will be stored in the CCR C3D clinical trials database. [name], the Principal Investigator, will be responsible for the protocol.
- The PI will be responsible for overseeing entry of data into an in-house password protected electronic system (C3D) and ensuring data accuracy, consistency and timeliness. The principal investigator, associate investigators/research nurses and/or a contracted data manager will assist with the data management efforts. Primary and final analyzed data will have identifiers so that research data can be attributed to an individual human subject participant.

All adverse events, including clinically significant abnormal findings on laboratory evaluations, regardless of severity, will be followed until return to baseline or stabilization of event. Patients will be followed for adverse events for 28 days (± 7 days) after removal from study treatment or until off-study, whichever comes first.

An abnormal laboratory value will be recorded in the database as an AE **only** if the laboratory abnormality is characterized by any of the following:

- Results in discontinuation from the study
- Is associated with clinical signs or symptoms
- Requires treatment or any other therapeutic intervention
- Is associated with death or another serious adverse event, including hospitalization.
- Is judged by the Investigator to be of significant clinical impact
- If any abnormal laboratory result is considered clinically significant, the investigator will provide details about the action taken with respect to the test drug and about the patient's outcome.

End of study procedures: Data will be stored according to HHS, FDA regulations, and NIH Intramural Records Retention Schedule as applicable.

Loss or destruction of data: Should we become aware that a major breach in our plan to protect subject confidentiality and trial data has occurred, this will be reported expeditiously per requirements in Section [7.2.1](#).

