1 INTRODUCTION

1.1 STUDY OBJECTIVES

1.1.1 Primary Objective:

- Assess the safety, tolerability and pharmacokinetics of pomalidomide at an oral dose regimen of 5mg once daily for 21 days of a 28 day cycle in subjects with Kaposi sarcoma, whether HIV associated or not, or in the case that the initial dosing schedule of pomalidomide is not tolerated, assess the safety, tolerability and pharmacokinetics of pomalidomide at 3mg daily for 21 days of a 28 day cycle.

1.1.2 Secondary Objectives:

- Explore in a preliminary manner the antitumor effect of pomalidomide at whichever of the dosing schedules described above is determined to be tolerable
- Assess the variation in pomalidomide pharmacokinetics in relation to common antiretroviral agents, especially potentially nephrotoxic agents such as tenofovir
- Assess changes in quality of life in subjects receiving pomalidomide
- Explore in a preliminary manner the safety, tolerability and antitumor effect of a second course of pomalidomide in patients who manifest KS requiring therapy after deriving clinical benefit from initial treatment with pomalidomide.

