In the phase 1b study in 24 patients with relapsed or refractory multiple myeloma([119](#)), 24 patients received a dose-escalating regimen of oral pomalidomide, administered continuously with arbitrarily defined 28 day cycles and commencing at a dose of 1mg daily (escalated to 2, 5, and 10mg). Dose limiting toxicities were assessed during the first four weeks of therapy. The most common drug-related toxicity was neutropenia, with grade 3/4 neutropenia occurring in 14 patients overall and increasing in a dose dependent manner. One deep venous thrombosis was observed in the DLT assessment timeframe, though this was probably due to unrelated melanoma developing in a groin lymph node, and three additional subjects developed thromboses after 4, 9 and 11 months of therapy respectively. No other severe (grade 3/4) non-hematologic toxicity was observed. Hematologic toxicity was less severe after the initial cycle, with the median time to grade 3/4 neutropenia in those experiencing this event being 3 weeks on therapy. The maximum tolerated dose in this population was 2mg daily continuous dosing.

A second arm of the phase 1b study (reported separately([132](#))) utilized the same dose levels (1mg escalated to 2, 5, and 10mg) but in an alternate-daily dosing schedule, again continuously for a 28 day 'cycle'. A further 24 patients were enrolled. The most common drug-related toxicity was again neutropenia, which was grade 3 in 6 of 17 patients (35%) treated at or below the 5mg dose level (with no grade 4 toxicity at these levels), and grade 4 in three patients, all at the 10mg alternate daily dose level. No other serious possibly drug-related adverse events were reported. The maximum tolerated dose in this population was therefore 5mg alternate daily.

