Based on these studies, the major serious adverse events appear to be reversible dose and schedule dependent hematotoxicity (most notably neutropenia with anemia and thrombocytopenia less frequent) and deep venous thrombosis (assessment of the frequency of which is complicated by high underlying rates of thrombosis in the malignancies studied), with other adverse events less common and generally mild. Patients with solid tumors were able to tolerate substantially higher total doses than those with hematologic malignancies. Prior cytotoxic exposure and patient PS also appear to influence the frequency and severity of adverse events. Cyclic or alternate daily dosing may reduce the severity of hematopoietic side effects while maintaining similar total dose delivery (for example, use of 5mg 21/28 days rather than 4mg continuously)([132-134](#)). Significant neurotoxicity (whether sedation, peripheral neuropathy, or otherwise) has not been observed. Serious adverse events reported to the sponsor from the ongoing studies mentioned above have been consistent with those published([108](#)). In light of the teratogenic effects observed in preclinical studies, all human studies have used stringent contraceptive guidelines.

[figure not shown]

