3.1.2 Dose Limiting Toxicity

For purposes of defining the toxic dose and as a basis of discussion for off-study criteria, the following is the definition of dose-limiting toxicity (DLT). It should be noted that neither pre-existing manifestations of HIV infection, nor of therapy for HIV infection, nor of KS (including bleeding from KS) will be considered dose-limiting. Dose limiting toxicities will be assessed over the first 8 weeks (2 cycles) of drug administration.

If a patient meets the criteria defined below, they will be considered as having dose-limiting toxicity.

- 3.1.2.1 Any grade 4 toxicity not including lymphopenia, CD4 lymphopenia, neutropenia, anemia and bilirubin or CK elevation that is at least possibly due to pomalidomide and is not attributable to HIV, its therapy or KS.
- 3.1.2.2 For lymphopenia, CD4 lymphopenia, neutropenia, or anemia and bilirubin or CK elevation additional restrictions apply to better separate drug effects from manifestations of HIV and/or its therapy. For these parameters, the definition of dose-limiting toxicity is as follows:
 - 3.1.2.2.1 For lymphopenia and CD4 counts, a decrease that (1) represents a grade 4 toxicity; (2) represents a 80% decrease from the entry value; (3) occurs in a patient with controlled HIV (<1,000 copies/mL); **and** (4) represents a 50 cell/mm³ decrease from entry will be considered dose-limiting if found to be present on two successive determinations. If a CD4 count meets the numerical criteria on one determination, it should be repeated at the next possible visit to see if it is confirmed.
 - 3.1.2.2.2 Neutropenia will only be considered dose-limiting if grade 4 for 14 days or more (including with G-CSF administration) or if grade 4 febrile neutropenia occurs.
 - 3.1.2.2.3 Anemia will only be considered dose limiting if grade 4 and other causes are not identified (for example, antiretroviral therapy with agents such as zidovudine).

- 3.1.2.2.4 For patients on HIV protease inhibitors who manifest hyperbilirubinemia, an increase total bilirubin of ≥ 5.0 mg/mL over baseline with an increase in indirect bilirubin of ≥ 4.5 mg/ml over baseline is considered dose-limiting. This is because bilirubin is frequently elevated in patients receiving these medications. This does not apply to patients whose HAART regimen does not include a protease inhibitor.

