3.3 DOSE MODIFICATIONS

All treatment modifications should be discussed with the senior clinical investigators on the study. Dose modification guidelines apply to the Phase 1 and Phase 2 portions of the study as well as the Second Optional Course of Therapy.

For Phase 1: Subjects who are enrolled on the initial (5mg) dose level who experience a DLT *not including a thromboembolic event* that resolves to grade 1 (or the grade they had at entry) *within*

28 days and continue to have KS may be considered for further therapy at the 3mg dose level if they continue to have KS requiring therapy. Response assessment for any such patients is described in Section **10.4**.

Table 1: Dose Modification of Pomalidomide

Event	Action	Resumption of Therapy
Neutropenia. ANC 500 to <1000 cells/mm ³ (CTCAE Grade 3)	*If observed during cycle (day 2 of cycle onward) therapy may continue with additional weekly CBCs. If observed day 1 of new cycle , therapy should be held. Consider G-CSF. (filgrastim) 5mcg/kg/daily SC rounded by $\pm 10\%$ to use the most economical combination of available products (commercial vials contain 300 mcg or 480 mcg). Pegylated filgrastim should not be used. Pomalidomide should not be administered during G-CSF treatment or within 24 hours after a G-CSF dose.	CBCs should be evaluated weekly and a new cycle of treatment may commence at the same dose level on or after day 29 once ANC ≥ 1000 cells/mm ³ .
Neutropenia. ANC <500 cells/mm ³ . (CTCAE Grade 4)	*Suspend or hold pomalidomide. Administer G-CSF (filgrastim) 5mcg/kg/daily SC rounded by $\pm 10\%$ to use the most economical combination of available products (commercial vials contain 300 mcg or 480 mcg). Pegylated filgrastim should not be used. Pomalidomide should not be administered during G-CSF treatment or within 24 hours after a G-CSF dose.	CBCs should be evaluated weekly and a new cycle of treatment may commence at the same dose level on or after day 29 once ANC ≥ 1000 cells/mm ³ so long as criteria for a DLT are not met.

Event	Action	Resumption of Therapy

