10.3 ACCRUAL TIMELINE

As the subjects being evaluated for toxicity may or may not be evaluable for response as part of the stringent eligibility response cohort, after an amendment to evaluate HIV positive and HIV negative patients in separate cohorts, the study may require enrolling from 25 to 40 subjects, depending on the final dose level and the number of those evaluated for toxicity that may also be evaluable for response.

It is anticipated that ten to twelve patients per year may enroll onto this trial. In order to allow for the possibility of a very small number of inevaluable subjects, the accrual ceiling will be set at 40 subjects. Accrual is expected to be completed within two to three years.

HAMB has an established cohort of KSHV-seropositive subjects, most with KS or a history of KS through protocol 01-C-0193 and other ongoing studies of KS, KSHV-MCD and KSHV-associated lymphoma as well as a referral base in the HIV and infectious disease community which together provide a population to support projected accrual. Accrual will be regularly reviewed against projections, and consideration given to additional promotional activities should it fall short of projections.

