10.4 STATISTICAL ANALYSES

An initial toxicity assessment phase of the trial will be conducted in which up to six subjects will be treated with pomalidomide at 5mg daily for 21 days of a 28 day cycle. If two or more subjects experience a DLT within the first two cycles (eight weeks), then up to six subsequent subjects will be treated at 3 mg daily for 21 days of a 28 day cycle. The highest dose at which zero or one of six subjects experience a DLT during the first two cycles (eight weeks) will be used to determine potential clinical activity.

Once the dose for assessment of clinical activity is determined, two expansion cohorts will be established to investigate response rate. These will be established with the goal of enrolling ten evaluable HIV negative patients, and fifteen evaluable HIV positive patients. Where KS is HIV-associated, these latter subjects will have somewhat more stringent entry criteria with respect to KS not responding to HAART to enable a better assessment of any anti-tumor activity uncomplicated by tumor responses associated with HAART initiation (inclusion criterion **2.1.1.15** above). Subjects treated at the dose chosen for assessment during the toxicity

assessment phase who met these additional eligibility criteria at study entry will be considered evaluable for response for this part of the study, in the appropriate cohort.

There are two circumstances under which an individual subject's dose could be de-escalated: first if two other subjects on the same dose level experience a DLT (Section 3.1.3), and second if the subject experiences a non-thromboembolic DLT on the higher dose level which resolves within 28 days (Section 3.3). In either instance, if the subject is evaluable they will be considered part of the initial (higher) dose cohort for the purposes of evaluating response.

At the dose for assessment of clinical activity, two cohorts of patients will be evaluated according to their HIV status as follows:

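### First-course safety is a primary objective, but untreated mid-cycle grade 3 neutropenia reaches the AE record only by investigator judgement, and section 10.4 plans no tabulation from the blood counts

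*Combined protocol and SAP*

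**What the plan says.** The primary objective (section 1.1.1) is to "Assess the safety, tolerability and pharmacokinetics of pomalidomide at an oral dose regimen of 5mg once daily", with 3 mg as the fallback. Section 1.2.3.4 sums up earlier experience by saying that "the major serious adverse events appear to be reversible dose and schedule dependent hematotoxicity", and singles out neutropenia, together with deep venous thrombosis.

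Four parts of the plan decide how neutropenia is counted:

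- **AE entry (section 6.1).** The rule begins "An abnormal laboratory value will be recorded in the database as an AE" and then restricts entry to five conditions: the value leads to discontinuation, comes with signs or symptoms, needs treatment or another intervention, accompanies a death or another SAE, or is in the investigator's judgement clinically important.
- **Dosing (section 3.3, Table 1).** For a neutrophil count of 500 to below 1000, "If observed during cycle (day 2 of cycle onward) therapy may continue with additional weekly CBCs". G-CSF is to be considered, not required. If the same count is found on day 1 of a new cycle, therapy is held. Below 500, pomalidomide is stopped or held and G-CSF is given.
- **DLT (section 3.1.2).** "Neutropenia will only be considered dose-limiting if grade 4 for 14 days or more", or if grade 4 febrile neutropenia occurs. Section 3.1.2.3.1 removes neutropenia from the general grade 3 rule. Section 3.1.2.5 adds a DLT if toxicity probably or definitely due to the drug prevents delivery on at least half of the scheduled days in cycles 1 and 2.
- **Analysis (section 10.4).** The first-course safety rule is the DLT count: "The highest dose at which zero or one of six subjects experience a DLT" over eight weeks sets the dose. No other first-course safety estimate, safety population or source for haematologic grades is named.

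**The concern.** A reader of the trial report will look to two counts for haematologic tolerability: DLTs and the AE table. Both can pass over the same event. A subject whose neutrophils fall to, say, 700 on day 15, who feels well, keeps taking the drug and gets no G-CSF is not a DLT and meets none of the four factual conditions for AE entry. Only the fifth condition, investigator judgement, remains. The study is open-label and no threshold is given to guide that judgement.

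At stake is how a primary objective is read. A low neutropenia rate in the AE table, beside few or no DLTs, could be taken as good haematologic tolerability when it partly reflects the entry rule.

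**Working it through.** **Step 1. Trace each presentation of neutropenia through the rules.**

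| Presentation | Table 1 action | DLT? | AE entry under 6.1? |
|---|---|---|---|
| Grade 3, mid-cycle, no symptoms, no G-CSF | Dosing may continue | No | Only by investigator judgement |
| Grade 3, mid-cycle, G-CSF given | G-CSF | No, unless 3.1.2.5 applies | Yes (treatment) |
| Grade 3, day 1 of a cycle | Therapy held, G-CSF considered | No, unless 3.1.2.5 applies | Yes if G-CSF is given; arguable if only held |
| Grade 4, under 14 days, no fever | Held, G-CSF given | No, unless 3.1.2.5 applies | Yes (treatment) |
| Grade 4 for 14 days or more, or grade 4 febrile | Held, G-CSF given | Yes | Yes |

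The gap is the first row. Section 3.1.2.5 does not help there, because dosing simply continues.

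**Step 2. When can the first row arise?** Sections 3.4.4.2 and 3.4.4.3 schedule counts on day 1 of every cycle and day 15 of cycles 1 to 3. Scheduled mid-cycle detection therefore falls mainly in cycles 1 to 3. Later mid-cycle cases would come from extra counts.

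**Step 3. A cohort from the documents.** The plan gives no figure for the under-count, so there is none to reproduce. The closest background rate is the alternate-day myeloma arm in section 1.2.3.4, where neutropenia was the commonest drug-related toxicity, "which was grade 3 in 6 of 17 patients (35%) treated at or below the 5mg dose level", with no grade 4 at those doses.

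- Rate: 6/17 = 0.353, which agrees with the stated 35%.
- Exact (Clopper-Pearson) 95% interval: Beta(0.025; 6, 12) to Beta(0.975; 7, 11) = 14.2% to 61.7%.
- Under this protocol's rules, those six subjects would give no neutropenia DLT (unless 3.1.2.5 applied) and anywhere from 0 to 6 AE entries.

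**Step 4. Illustration of size.** Recorded rate = true rate × share of affected subjects who meet an entry condition. The share is an assumption, since the documents give none. For the counts, 25 treated is the lower figure in section 10.3 ("the study may require enrolling from 25 to 40 subjects"), so 25 × 6/17 = 8.8 subjects are expected to be affected.

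| Share recorded | Recorded rate at a true 35.3% | Expected subjects recorded, of 8.8 affected |
|---|---|---|
| 100% | 35% | 8.8 |
| 75% | 0.353 × 0.75 = 26% | 6.6 |
| 50% | 0.353 × 0.50 = 18% | 4.4 |
| 25% | 0.353 × 0.25 = 9% | 2.2 |
| 0% | 0% | 0 |

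If the true rate in Kaposi sarcoma is near zero, the gap is near zero at any share.

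**The case against.** The strongest reply is that section 6.1 limits what is coded as an AE, not what is collected. The blood counts are scheduled, complete records are kept (outside laboratory results included), and nothing says that haematologic toxicity will be tabulated from AE entries alone. This stands. A reader might infer that safety will be understated, but the documents support only that it could be. The reply does not supply the missing plan, though: 10.4 never says that the counts feed a toxicity table.

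Second, there are several routes into the AE record. The Table 1 footnote expects some grade 3 cases to need G-CSF. A hold on day 1 may count as an intervention. Adverse events and participants are discussed weekly (sections 6.3 and 7.4.1), and section 8.1.1 defines AEs to include abnormal laboratory findings. These points narrow the gap to the untreated mid-cycle case. They do not close it, because 6.1 is the operative entry rule and is narrower than 8.1.1.

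Third, the 35% comes from myeloma on another schedule. Section 1.2.3.4 says that patients with solid tumours tolerated substantially higher doses, and no significant neutropenia was seen in 44 prostate cancer patients at 1 or 2 mg. Other solid-tumour cohorts in that section did show it, including dose-limiting neutropenia at 5 mg continuous dosing. The rate here is uncertain, so the figures above illustrate the mechanism and do not forecast it.

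Fourth, the DLT definition is deliberate. Section 3.1.2.2 explains that the restrictions separate drug effects from HIV and its therapy. That is accepted.

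**Conclusion.** The point holds as a gap in the analysis plan. Followed as written, the rules make the recorded frequency of untreated mid-cycle grade 3 neutropenia depend on investigator judgement, and 10.4 names no estimate that avoids this. A first-course summary built on AE entries could understate the drug's main expected toxicity. The size cannot be found from the documents: it depends on the true rate in this population and on the share of cases that meet an entry condition, and it could be nil or large.

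A reader might go further and infer that the phase I result is unsafe, that 5 mg was wrongly chosen or that the DLT definition is defective. The documents do not support that. Section 3.1.5 reports no DLTs in the first six subjects, and the stated rule was correctly applied to that result. Nor is grade 4 neutropenia lost, because Table 1 requires G-CSF and so brings it into the AE record. No response threshold, sample size or error rate is affected.

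**What to change.** Add a paragraph to section 10.4:

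- Neutrophils, platelets and haemoglobin will be graded by CTCAE v4.0 from all on-study blood counts, including extra counts and outside laboratory results, whether or not an AE was entered.
- The population is all subjects given at least one first-course dose at 5 mg.
- The report is worst grade per subject over the first course, with exact 95% confidence intervals, and shift from baseline.
- The section 6.1 rule stays for AE entry but does not define the laboratory toxicity rate.

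Platelets and haemoglobin are included because the same entry rule governs them.

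The cost is one derived table from counts already drawn. The downside is that falls due to HIV, its therapy or benign ethnic neutropenia (section 1.2.4.2) are counted as well. The baseline shift helps to show these. Sections 2.1.1.8.3 and 3.4.3 require a neutrophil count of at least 1000 at entry and again within 24 hours before the first dose, so a later grade 3 value is a new fall below that level, whatever its cause. The table cannot show a nadir on a day when no count was drawn.
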